## 4.1.3 Baseline and Change from Baseline

In general, the baseline for this study (with the exception of physical examination) will be taken as the latest pre-dose measure on Study Day 1 (i.e. prior to the first dose for all cohorts). If this is missing then the screening value, or, if available, a pre-dose unscheduled measurement will be used (whichever is closer to the baseline date). For physical

examination, the baseline assessment will be considered as the Screening Visit 1.

Unless indicated otherwise change from baseline (CFB) will be calculated as follows:

CFB = Visit Result – Baseline Result

Percent change from baseline (PCFB) will be calculated as follow: PCFB (%) = 100\*(Visit Result – Baseline Result)/Baseline Results

### 4.2 Analysis Sets

After all the data have been verified/coded/entered into the database, a review will be performed by DP Clinical, Inc (DPC) and the sponsor. The purpose of this review will be to define the analysis sets. The review will also check the quality of the data, identifying outliers, and making decisions on how to deal with problems in any data (e.g., missing values, withdrawals, protocol deviations). After the pre-analysis review, resolution of all issues and documentation of all decisions, the database will be locked.

#### Screened Set:

The Screened Set will include all subjects who signed the informed consent form and were screened for participation in this study. This set will be used only for the purpose of describing study disposition.

## Safety Population / Intent-to-Treat (ITT) Set:

The Safety Set will include all subjects who receive at least one dose of study medication. The ITT Set will be identical to the Safety Set for this study. All baseline characteristics, demographic and efficacy endpoint data will be presented using the ITT Set.

## Per Protocol (PP) Set:

The PP Set will include subjects who complete Part A Core Study Phase (Visit 15) and who have not violated any inclusion or exclusion criteria and/or deviated from the protocol in a way that could influence their efficacy assessment through Visit 15. Decisions concerning the exclusion of subjects from this set will be made and documented during an adjudication by DPC and the sponsor prior to database lock. Baseline characteristics, demographics and efficacy endpoint data will be presented using the PP Set.

#### Pharmacokinetic (PK) Set:

The PK Set will include all subjects in the Safety Set who have at least one evaluable non-BLQ post-dose PK measurement.

#### Pharmacodynamic (PD) Set:

The PD Set will include all subjects in the Safety Set who have at least one evaluable post-dose PD measurement.

## 4.3 Test Hypothesis and *P*-Value Justification

No formal inferential statistics will be applied to data collected in this study.

## 4.4 Procedures for Handling Missing Data and Dropouts

A missed visit and assessment details eCRF page will summarise which visits / assessments were missed along with the reason (e.g., COVID-19, or other). This will be listed for both Part B and Overall Study.

#### 4.4.1 Safety Data

Where appropriate, screening values may be used as baseline in the event of missing or unusable Day 1 measurements. No imputation of missing data for early terminations will be performed.

However, both partial and completely missing dates/times that are not related to early terminations, in addition to missing safety data (e.g., missing severities) will be reviewed on a case by case basis for potential imputations. As a general

rule, a conservative approach will be adopted as outlined in Section 5.2.1 (e.g. partial Adverse Event (AE) onset dates and missing severities will be taken as the earliest 'on treatment' start date and highest severity, respectively, consistent with the partial information available). Moreover, the original data, without imputations, will be presented separately in data listings.

For safety lab parameters that are below or above the limit of quantification, the data will be presented as-is in the listings, but the limit of quantification will be used for the purposes of calculating change from baseline.

#### 4.4.2 PK and Efficacy/PD Concentration Data

APL-2 concentrations reported from pre-dose on Day 1 to the time of the first quantifiable value will be taken as zero for linear plots and the calculation of PK parameters, and equal to the lower limit of quantification (LLOQ) for semi-logarithmic plots.

After this time point, concentrations below the limit of quantification (BLQ) will be set to zero, with the exception of the calculation of the geometric mean where the LLOQ will be used.

If a BLQ value falls between two quantifiable concentrations the value will be set equal to the LLOQ, unless its exclusion can be justified (e.g. implausibility given the profile observed and known PK properties).

In the event of a missing PD baseline value a screen measurement or pre-dose unscheduled measurement may be used (whichever is closer to the baseline date).

If a baseline PD value is zero, then the percent change from baseline will not be calculated. If a post baseline value is BLQ, then the value will be set to the LLOQ. Similarly, for PD plots, a BLQ value will be set equal to LLOQ.

## 4.5 Interim Analysis

One interim analysis is planned when all subjects enrolled in the study have completed Part A, the Core Study Phase (screening to day 336) or discontinued prior to Day 336. The interim analysis will present all planned tables, listings, and figures (TLF) listed in Appendix 8.1 for only the Part A Core Study Phase. The data will consist of:

- For subjects who rollover into the Part B Extension Phase, all data collected through the date of Visit 15 will be included. For occurrence data, such as Adverse Events and Concomitant Medications, records with a start date on or before the Visit 15 (which is considered the start of dosing date for the extension phase) will be included.
- For all subjects who do not rollover into the Part B extension Phase (i.e. who discontinue during the Part A Core Study Phase), all data will be included.

## 4.6 Subgroup Analysis

Due to the small sample size of the study, no subgroup analyses will occur.

## 4.7 Multi-Center Studies and Pooling of Centers

This is a multi-center study. Due to the small number of subjects at each site, no adjustments will be made for study site.

## 5. STATISTICAL ANALYSIS METHODOLOGY

In general, tables will be presented by randomized dose level within cohort (270 mg vs. 360 mg) and by cohort.

Tabulations for continuous data will use a standard set of descriptive statistics: number of observations available (n), mean, standard deviation (SD), median, and range (minimum, maximum).

Categorical or dichotomous data will be tabulated using frequencies (counts and percentages). The numerator and denominator for each percentage calculation will be specified in the footnotes of table shells.

Data listings will present all information recorded in eCRFs for all subjects and visits. All listings will be sorted by cohort and subject number.

Unless otherwise noted, tabulations or descriptive statistics by visit during the Part A Core Study Phase will include only scheduled visits through Visit 15 (i.e. summary statistics will not include follow-up Visits 16 and 17.

## 5.1 Study Subjects

## 5.1.1 Subject Disposition

The following disposition categories will be tabulated by randomized dose level within cohort (for categories after enrollment) and by cohort:

- Number of subjects screened
- Number of screen failures with reason for screen failure
- Number of subjects who receive at least at least one dose of APL-2
- Number of subjects with at least1 non-BLQ post-dose PK assessment
- Number of subjects with at least 1 post-dose PD assessment
- Number of subjects who complete Part A Core Study Phase subjects who complete through Visit 15
- Number of subjects in the PP set per definition in Section 4.2

- Number of early termination subject during Part A Core Study Phase with reason for early termination – subjects who do not complete Visit 15
- Number of subjects who rollover to Part B Long Term Extension Phase
- Reason for Withdrawal during Part B Long Term Extension Phase (Final Analysis Only)

## 5.1.2 Protocol Deviations

A protocol deviation is any change, divergence, or departure from the study design or procedure defined in the protocol.

The following categories will be used to group protocol deviations:

- 1. Eligibility Not Met
- 2. Study Assessment Noncompliance
- 3. Study Drug Noncompliance
- 4. Study Schedule Noncompliance
- 5. Other

The following are categorical reasons used to document why a protocol deviation occurred:

- 1. Subject Illness
- 2. Subject Unable to Comply
- 3. Subject Refusal
- 4. Clinical/Site Error
- 5. Laboratory Error
- 6. Investigator/Staff decision
- 7. Other

Subsets of the protocol deviations can be identified as major and minor protocol deviation as described below:

Major Protocol Deviation: A protocol deviation that might significantly affect the completeness, accuracy, and/or reliability of the study data or that might significantly affect a subject's rights, safety, or well-being.

Minor Protocol Deviation: A protocol deviation that will not significantly affect the completeness, accuracy, and/or reliability of the study data and that will not significantly affect a subject's rights, safety, or well-being.

Upon soft lock of database, all documented protocol deviations in the study will be reviewed to identify all major and minor protocol deviations by a data review team including representatives from DPC clinical operations, medical, data management, and statistics, and sent to the sponsor for approval. Final decisions will be documented and incorporated into the ADaM Data Structure for Protocol Deviation Analysis (ADDV) dataset.

Protocol deviation data will be presented for the safety set. Protocol deviation data will be listed. Additionally, the number of deviations and number/proportion of subjects with protocol deviations and with major protocol deviations will be tabulated by randomized dose level and by cohort. The number of deviations and number/proportion of subjects with each protocol deviation category will also be tabulated by randomized dose level and by randomized dose level and by cohort.

### 5.1.3 Medical and Surgical History

All medical/surgical history data and ongoing medical history will be summarized by the Medical Dictionary for Regulatory Activities (MedDRA) version 20.0 System Organ Class (SOC) and Preferred Term (PT) and by randomized dose level and by cohort.

## 5.1.4 Prior and Concomitant Medications

Prior and concomitant medications will be coded to the therapeutic drug classes and generic drug names using the World Health Organization (WHO) Drug Dictionary (WHODrug) classifications version March 2017.

Prior medications will include any medications reported with a start date prior to the subject taking their first study dose and will be summarized by WHODrug Anatomical Therapeutic Chemical (ATC) Class 3 Term and WHODrug Preferred Name. Concomitant medications will include any medications being taken after the subject starts their study medication and will also be summarized by WHODrug ATC Class 3 Term and WHODrug Preferred Name. Hence, medications ongoing at the start of dosing will be counted in both the prior and concomitant medication summaries.

For the purposes of determining prior and concomitant medications, if a partial date is recorded, the following convention will be used to assign the medication dates:

- If a start date is missing the day information and month/year is the same as first dose date then use first dose date, else '01' will be used for the day; if a start date is missing the month and the year is the same as first dose date then use first dose date, else January will be used for the start month.
- If a stop date is missing the day information and month/year is same as last study date then use last study date, else last day of the given month will be used for the stop day; if a stop date is missing the month and year is the same as last study date then use last study date, else December will be used for the stop month.

All prior medications and concomitant medications, interventions and procedures will be summarized in listings. The frequency of subjects taking prior medications and concomitant medications will be tabulated

by WHODrug ATC Class 3 and Preferred Name, and by randomized dose level and by cohort.

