## 5.2.1 Adverse Events

TEAEs are defined as those AEs that occur after Dosing on Day 1, or worsen in severity, and up to 30 days after the last dose of APL-2. For subjects who rollover to Part B long term extension phase, any AE recorded on the date of Visit 15 (start of dosing for the extension phase) will be included in Part A. Version 20.0 of MedDRA will be used to classify all AEs.

AEs will be considered treatment-emergent (TEAE) unless there is clear indication that the event occurred prior to first dose of study drug. AEs present prior to the first dose of study drug administration that increased in severity or relationship to study drug after the first dose of study drug and up to 30 days beyond the last dose of study drug will be classed as a TEAE. Events with missing or partial dates will be handled such that in the absence of contradictory information an AE is treatment emergent. So, for a missing start date (where stop date is after date of first dose) the date will be imputed as the date of first dose; for a missing stop date the date will be imputed as the last study date. If a partial date is recorded, the following convention will be used to assign the AE:

If a start date is missing the day information and month/year is the

same as first dose date then use first dose date, else '01' will be used for the day; if a start date is missing the month and the year is the same as first dose date then use first dose date, else January will be used for the start month.

• If a stop date is missing the day information and month/year is same as last study date then use last study date, else last day of the given month will be used for the stop day; if a stop date is missing the month and year is the same as last study date then use last study date, else December will be used for the stop month.

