#### 5.1.5 Prior and Concomitant Medications

#### 5.1.5.1 **Prior and Concomitant Derivations**

Prior and concomitant medications will be coded to the therapeutic drug classes and generic drug names using the World Health Organization (WHO) Drug Dictionary (WHODrug) classifications version March 2021.

Prior medications will include any medications reported with a start date prior to the subject taking their first study dose of Part A Core Study and will be summarized by WHODrug Anatomical Therapeutic Chemical (ATC) Class 3 Term and WHODrug Preferred Name.

Concomitant medications (CM) will include any medications being taken after the subject starts their study medication and will also be summarized by WHODrug ATC Class 3 Term and WHODrug Preferred Name. Hence, medications ongoing at the start of dosing will be counted in both the prior and concomitant medication summaries. Further categorization for concomitant medications will be included in the analysis:

- Part A + B CM: Any medication taken during Part A or Part B of the study. This can include prior medications that were continued into Part A and Part B of the study
- Part B CM: Any medication taken during Part B of the study. This can include prior medications that were taken continuously into Part B of the study. Concomitant medications taken in Part A but ended prior to Part B will not be considered as concomitant medications during Part B.

For the purposes of determining prior/concomitant medications and study part, if a partial date is recorded, the following convention will be used to assign the medication dates:

• If a start date is missing the day information and month/year is the same as first dose date then use first dose date, else '01' will be used

for the day; if a start date is missing the month and the year is the same as first dose date then use first dose date, else January will be used for the start month.

• If a stop date is missing the day information and month/year is same as last study date then use last study date, else last day of the given month will be used for the stop day; if a stop date is missing the month and year is the same as last study date then use last study date, else December will be used for the stop month.

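### The medication date rule sets some partial start dates to the first-dose date without looking at the stop date, so drugs finished before dosing, or ongoing at dosing, are put in the wrong descriptive table or in none

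*SAP*

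**What the plan says.** Part A SAP 5.1.4 (Prior and Concomitant Medications) defines the two groups as follows:

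- Prior: "Prior medications will include any medications reported with a start date prior to the subject taking their first study dose".
- Concomitant: "Concomitant medications will include any medications being taken after the subject starts their study medication".

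It draws the consequence that a drug in use when dosing begins is counted in both summaries. It then gives a convention for partial dates:

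- Start, day missing: "If a start date is missing the day information and month/year is the same as first dose date then use first dose date"; otherwise day 01.
- Start, month missing: "if a start date is missing the month and the year is the same as first dose date then use first dose date"; for any other year the start is placed in January.
- Stop, day missing: the last study date if month and year match it, "else last day of the given month will be used for the stop day".
- Stop, month missing: the last study date if the year matches it, otherwise December.

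No start-date clause refers to the stop date.

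Part B SAP 5.1.5.1 (Prior and Concomitant Derivations) repeats the convention and also uses it to assign study part. Its definition is the same in substance: "Prior medications will include any medications reported with a start date prior to the subject taking their first study dose of Part A Core Study".

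**The concern.** The rule leans towards treating an event of uncertain date as on-treatment. That is a cautious choice for adverse events. It does not suit a split into prior and concomitant drugs, because pulling an uncertain start forward to the first dose removes the drug from the prior group by construction. If the drug is known to have stopped before dosing, the imputed start also falls after the recorded stop.

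What is at stake is the description of recent treatment before APL-2. The wAIHA cohort is defined by failure or intolerance of at least one earlier regimen (Protocol 10.1, criterion 10), so readers of the report will look at the prior-medication table. A steroid course given and finished in the months before dosing could be absent from it, or could be shown as given alongside APL-2.

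**Working it through.** The plan states no figure to reproduce, so the check applies the rule literally.

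**Inputs.** The definitions and date rules are those of Part A SAP 5.1.4. Prior is coded as start < first dose, and concomitant as stop on or after first dose. Two dates are assumed for illustration: first dose 15 Sep 2018 and last study date 8 Nov 2019. The second is 419 days later, matching a Day 420 Exit Visit.

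| Recorded start | Recorded stop | Imputed start | Imputed stop | Prior | Concomitant |
|---|---|---|---|---|---|
| 2018 | 31 Mar 2018 | 15 Sep 2018 | 31 Mar 2018 | no | no |
| 2018 | Mar 2018 | 15 Sep 2018 | 31 Mar 2018 | no | no |
| Sep 2018 | 10 Sep 2018 | 15 Sep 2018 | 10 Sep 2018 | no | no |
| 2018 | 2018 | 15 Sep 2018 | 31 Dec 2018 | no | yes |
| Sep 2018 | Sep 2018 | 15 Sep 2018 | 30 Sep 2018 | no | yes |
| 2018 | ongoing | 15 Sep 2018 | none | no | yes |
| Mar 2018 | 31 Mar 2018 | 1 Mar 2018 | 31 Mar 2018 | yes | no |
| 2017 | 31 Mar 2018 | 1 Jan 2017 | 31 Mar 2018 | yes | no |

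- Rows 1 to 3: the imputed start is later than the stop, and the record is in neither table.
- Rows 4 and 5: a drug that may have ended before dosing is shown as concomitant only, because the stop rule pushes its end past the first dose.
- Row 6: if the drug is known to have been in use at first dose, the section says it belongs in both summaries; the rule leaves it in one.
- Rows 7 and 8: a known earlier month or an earlier year is classified correctly.

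**All year-only starts.** Put the first dose on the 15th of each month of a 365-day year. Combine a year-only start in that year with every possible complete stop date before dosing. The number of stop dates is 14 + 45 + 73 + 104 + 134 + 165 + 195 + 226 + 257 + 287 + 318 + 348 = 2166. All 2166 lose prior status.

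**How much pre-dose time is exposed.** For year-only starts this depends on the first-dose date, which is an assumption. Of the 365 days before first dose, the share in the same calendar year is:

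- 15 January: 14/365 = 3.8%
- 30 June: 180/365 = 49.3%
- 15 December: 348/365 = 95.3%

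**Weight of one subject.** Part A plans up to 12 per cohort and up to 6 per dose group: 1/12 = 8.3 points and 1/6 = 16.7 points. The tables count subjects, so a row moves only if no other record already places that subject in it.

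**Effect of a stop-date condition alone.** Keep the first-dose date only when the imputed stop is not before first dose; otherwise use day 01 or 1 January. Rows 1 to 3 become prior only, with start no later than stop. Rows 4 to 6 do not change, so that condition is not enough by itself.

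**The case against.** Several points on the other side stand.

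- **Narrow reach.** Starts in an earlier year or a known earlier month are handled correctly. Only starts in the first-dose year (month unknown) or first-dose month (day unknown) are exposed. The documents do not show how many such records exist.
- **Concomitant status.** A reader might infer that any finished drug caught by the rule is shown as given with APL-2. The text does not support that. A drug with a complete stop before dosing is not being taken afterwards, whatever its imputed start, so it lands in neither table. Concomitant status needs a partial stop date that the stop rule moves past the first dose.
- **The AE comparison.** A reader might also infer that the adverse-event section has a safeguard that the medication section dropped. Part A SAP 5.2.1 does say "for a missing start date (where stop date is after date of first dose) the date will be imputed as the date of first dose", but that covers a wholly missing start. Its partial-date clauses match those for medications and carry no such condition.
- **Importance.** Eligibility is decided at screening, not from this table. Steroid and rituximab history is collected at screening (Protocol 12.1), and the documents do not say whether it feeds this table. The haemoglobin baseline is a measured value. No test or subgroup analysis uses the table.
- **Mitigation.** Protocol 15.2.6 and Part A SAP 4.4.1 provide case-by-case review of missing dates and show unimputed data in listings. All prior medications are listed, so with at most 24 planned subjects an impossible date could be spotted.

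The last point does not rescue the rule. Review and listings do not amend an explicit convention, and the frequency tables would still follow it.

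**Conclusion.** Wrong as written, at low severity. This is a stated rule that gives a wrong classification, not a missing detail. It has three consequences: loss from both tables when a complete stop date precedes dosing, possible concomitant-only status when the stop is also partial in the first-dose year or month, and loss of prior status for a drug known to be ongoing at first dose. The third contradicts the section's own statement.

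The effect is confined to descriptive medication tables. Inferring harm to wAIHA eligibility, to the haemoglobin baseline or to the primary safety endpoint would go beyond the documents. The 8.3 and 16.7 points hold for Part A at its planned maximum sizes; a smaller group would give one subject more weight. They do not carry over to Part B, which tabulates by cohort among subjects who rolled over. The conclusion rests on a literal reading of the convention; its practical size depends on the unknown number of partial records and on first-dose dates.

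**What to change.** Make the same change in Part A SAP 5.1.4 and Part B SAP 5.1.5.1:

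1. Set a partial start to the first-dose date only if the stop is missing or falls on or after first dose, and the drug is not known to have been ongoing at first dose. Otherwise use day 01 of the known month or 1 January of the known year.
2. Classify a drug known to have stopped before first dose as prior only, and a drug known to be ongoing at first dose as both prior and concomitant, whatever the imputed start.
3. Add a rule for partial stop dates that could precede first dose, for example an indicator that the drug ended before first dose, if the eCRF collects one. If it does not, state how such records are classified and footnote their number.
4. Add a program check that no imputed start is later than a recorded stop.

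The cost is a few sentences in each SAP and a few program lines. Items 1, 2 and 4 need no new data; item 3 depends on what the eCRF holds. If tables have already been produced, rerun the medication summaries and report the number of records that change.
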